### **Study Timeline**

The study timeline for research procedures with a subject is the length of their surgical case in PSU. The only additional time needed on top of their standard of care visits is the time needed to complete an informed consent discussion at the initial examination appointment.

### **Data to be Collected for your study (AFTER consent and HIPAA Authorization have been obtained)**

Age, medical history, diagnosis, vital signs, behavioral pain scale.

### **Data Analysis Plan**

To assess compare the changes of vital signs, pain scores between buffered and conventional local anesthesia, we will use independent t-tests (SPSS v25). We considered a P-value of 0.05 or less significant.

The variability in measurements in this dental surgical population is currently unknown, therefore a power analysis is not appropriate. The data from this study will provide the necessary information to perform a power analysis for a future, larger trial.

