## **Objectives**

The aim of this study is to compare physiological responses in children during the administration of buffered (with sodium bicarbonate) versus non-buffered local anesthetic (LA) control by recording and comparing changes in vital signs and physical movements in pediatric patients undergoing a dental procedure under deep sedation.

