## **Background**

The ability to manage pain for the pediatric patient during routine dental procedures can have a profound effect on the child's behavior during current and future appointments. Many adults with dental fears and anxiety recall experiencing negative dental experiences during childhood. However, it is difficult to determine whether successful pain management is achieved in children due to their emotional or cognitive developmental levels. Younger children are often unable to provide reliable feedback on a self-reported pain scale when asked to rate their pain perception. The body's response to stress and anxiety during administration of LA can be detected by changes in physiological responses, such as blood pressure (BP), heart rate (HR) and respiratory rate (RR). The anesthesiology team routinely responds to the child's vitals and movements, that if triggered by pain during the injection of a local anesthetic, may lead to administration of additional sedative medications during treatment. Therefore, by monitoring changes in vital signs during the administration of local anesthetic agents may be more reliable to represent the level of pain that a child receives.

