## **Study Design**

This is a prospective, single visit, randomized, double-blind split mouth study.

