## **Study Procedures**

I. All standard of care dental procedures will be followed for enrolled patients except as noted below:

1. IDS will dispense two types of local anesthetic solutionsto dental providers blindly: control solution (non-buffered LA, 2% lidocaine with epinephrine 1:100,000)) and test solution (buffered LA). Both types of solution will be administered to each subject. The types of solutions are labelled with numbers and the research team will remain blind to the type until the study is over.

2. The test solution will be made by a mixing pen called "Onset" (Onpharma Inc., Los Gatos, CA., USA), which is an FDA- approved device (see attachments). IDS will use a cartridge of 2% lidocaine with epinephrine 1:100,000 alkalinized at 9:1 ratio with a resulting pH of 7.21 using 8.4% sodium bicarbonate solution per manufacturer. This mixing pen Onset will deliver 0.18 mL of sodium bicarbonate solution into the anesthetic cartridge.

3. A dental provider will use a randomized coin flip to choose between the blindly labeled anesthetic agents to anesthetize one side of the mouth (left vs right). In addition, the sides of mouth will also be randomly selected by the toss of a coin. After the appropriate blind anesthetic solution has been selected, the same solution will be used to anesthetize each side of the mouth. In general, one cartridge of local anesthetic is sufficient to provide adequate anesthesia for 2 quadrants, however IDS will provide 2 cartridges of each solution in the event that a second cartridge of the same solution is needed. Maximum recommended dosage for local anesthetic will be calculated and followed for each patient. The provider will subsequently anesthetize the opposite side of the mouth with the opposite solution. The sequence used to administer the anesthetic will be inconsequential as the evaluation of pain will remain consistent due to the separation of nerve innervations in the posterior jaw.

4. Two researchers are required to present for each study. One researcher will be the provider who administrates LA and the other will be recording vital signs and physical movements during the injection (see point IV below).

II. In PSU, patients will be monitored per standard of care. This study does not cause potential interference with sedation monitoring.

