III. The only additional device used in this study is Onset mixing system. The Onset device is already FDA-approved for pH buffering dental local anesthetic agents with sodium bicarbonate (see attachments).

IV. Data for this study will come from the EMR, the SDM, and intra-operative data collection sheets.

1. Vital signs, which are already recorded per standard of care at baseline and every 5 minutes, will be recorded manually for significant operative events by researchers on an intra-operative data collection sheet. Significant operative events includes: topical anesthesia, injection (needle puncturing the oral mucosal tissues), delivery of both buffered and conventional local anesthesia, surgical procedures (including tooth preparation, pulpal treatment, and tooth extractions). The necessity of additional local anesthesia delivery will also be noted.

2. Modified Behavioral Pain Scale (BPS) and Pediatric Sedation State Scale (PSSS) are valid and reliable tools in the assessment of pain in the unconscious sedated patient and monitor patient's comfort level during sedation, will be recorded on intra-operative data collection sheet by study personnel during the significant operative events as listed above. We removed the ventilation compliance in BPS form since this is not applicable in our study.

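### Additional sedative may be given in response to the signs being compared, but its time and amount are not named as data and the analysis does not say which readings are compared

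*Combined protocol and SAP*

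**What the plan says.** The Background section says the anesthesiology team reacts to the child's vital signs and movements, "that if triggered by pain during the injection of a local anesthetic, may lead to administration of additional sedative medications during treatment". The Objectives describe the study as "recording and comparing changes in vital signs and physical movements in pediatric patients undergoing a dental procedure under deep sedation". The signs that may prompt more sedative are therefore the signs being compared.

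The design is a "prospective, single visit, randomized, double-blind split mouth study". One side is injected first; then, in Study Procedures I.3, "The provider will subsequently anesthetize the opposite side of the mouth with the opposite solution". Coin tosses choose the solution and the side. The same item calls the sequence "inconsequential as the evaluation of pain will remain consistent due to the separation of nerve innervations in the posterior jaw". It also supplies spare cartridges "in the event that a second cartridge of the same solution is needed".

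Study Procedures IV names the EMR, the SDM and intra-operative sheets as sources. IV.1 lists the events at which vital signs are recorded: topical anesthesia, needle puncture, delivery of the solution, and "surgical procedures (including tooth preparation, pulpal treatment, and tooth extractions". The need for more local anesthetic is noted. IV.2 adds a modified Behavioral Pain Scale and the Pediatric Sedation State Scale (PSSS) at the same events. The data list names age, medical history, diagnosis, vital signs and the behavioral pain scale. Neither place names additional sedative.

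The Data Analysis Plan reads: "To assess compare the changes of vital signs, pain scores between buffered and conventional local anesthesia, we will use independent t-tests (SPSS v25". It does not say at which events a change is measured, or how readings after additional sedative are treated.

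**The concern.** Additional sedative given because of a reaction is a consequence of the outcome, and it can alter every later reading in that child. If the less comfortable solution provokes more reactions, it also attracts more sedative, and later readings on that side are quieter for a reason unrelated to the local anesthetic. Because both sides are treated in one visit under systemic sedation, a dose prompted by the first side may still be acting when the second is injected.

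The protocol's reason for setting sequence aside is that the two sides have separate nerve supply. That is an argument about the local anesthetic; it does not reach a drug acting on the whole child.

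At stake is whether a difference, or its absence, can be interpreted. Without the time and amount of each additional dose, and the order of sides and solutions, the analyst cannot tell which readings preceded sedative and which followed it. Additional sedative by solution would also be informative in itself, since the Background section presents it as a possible result of injection pain.

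**Working it through.** **Which readings are meant.** The Objectives and the end of the Background section frame the comparison as responses while the local anesthetic is being given. Study Procedures I.4 has the second researcher recording during the injection. These point to the puncture and delivery readings. But I.4 refers on to point IV, whose events run through to surgery, and the Data Analysis Plan does not choose among them.

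**How each kind of reading can be affected.**
- First-side puncture and delivery: unaffected only if no sedative is given between puncture and delivery. IV.1 lists these as separate events, and I.3 allows for two quadrants and a second cartridge, so the text does not rule it out.
- Second-side puncture and delivery: may be damped by sedative prompted by the first side. This enlarges the apparent benefit when control goes first and shrinks it when buffered goes first.
- Surgical events: may follow sedative prompted by the same side's injection, which pulls toward no difference.

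**Illustration, all inputs assumed.** The plan has no figure to reproduce; it gives 20 children but no effect size or SD. Let C and B be heart-rate rises at injection (control, buffered), normal with means 12 and 7 bpm, SD 8, correlation 0.5; the true difference is 5.0. Additional sedative follows a rise above T, after the delivery reading, and multiplies later responses by (1 − d). For a response X with correlation 0.5 to the triggering rise Y:

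E[X·1(Y>T)] = mean_X × P(Y>T) + 0.5 × 8 × φ((T − mean_Y)/8)

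*Injection, T = 12.* E[B·1(C>12)] = 7 × 0.5000 + 4 × 0.3989 = 5.10. E[C·1(B>12)] = 12 × 0.2660 + 4 × 0.3282 = 4.50. With d = 50%:
- control first: 5 + 0.5 × 5.10 = 7.55
- buffered first: 5 − 0.5 × 4.50 = 2.75
- even order: (7.55 + 2.75)/2 = 5.15

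*Surgical, same-side damping only, T = 12.* The surgical response has the same means and SD, and correlation 0.5 with its own side's injection rise. Control: 12 × 0.5000 + 4 × 0.3989 = 7.596. Buffered: 7 × 0.2660 + 4 × 0.3282 = 3.175. Estimate = 5 − d × (7.596 − 3.175) = 5 − 4.421d.

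| T (bpm) | Injection, even order, d = 10/30/50% | Surgical, same side, d = 10/30/50% |
|---|---|---|
| 12 | 5.03 / 5.09 / 5.15 | 4.56 / 3.67 / 2.79 |
| 15 | 5.05 / 5.16 / 5.27 | 4.63 / 3.90 / 3.17 |
| 18 | 5.06 / 5.17 / 5.29 | 4.73 / 4.19 / 3.64 |

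*Against sampling error.* The within-child difference has SD 8 × √(2 × (1 − 0.5)) = 8, so its standard error with 20 children is 8/√20 = 1.79. The injection bias of 0.03 to 0.29 bpm is 0.02 to 0.16 of that.

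*Order.* Fair coin tosses need not split evenly: 2 × P(Bin(20, 0.5) ≤ 7) = 0.263 for 13–7 or more uneven. At T = 12, d = 50%, seven control-first children give 0.35 × 7.55 + 0.65 × 2.75 = 4.43, and thirteen give 0.65 × 7.55 + 0.35 × 2.75 = 5.87. This is chance, not systematic bias. Adjusting for whether a side came first or second weights the two orders equally and so targets the even-order value whatever the split.

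**The case against.** The strongest reply is that the documents already point to the injection reading, and that there the expected bias is small. That largely stands: with even order the illustration gives at most 0.16 of a standard error. The attenuation arises in surgical-event readings, and nothing states that these are combined with injection readings. A reader might infer from the plan's silence that all events will be averaged and the treatment effect diluted. That is a possible reading of an unspecified analysis, not a stated plan.

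A reader might also infer that a distorted SD would pass into the future trial's power analysis. This is not shown. The planned independent t-test yields a per-solution SD; simulating the injection model above gives 7.3 to 7.9 against 8.0. With 20 values and a true SD of 8, 95% of sample SDs lie between 8 × √(8.907/19) = 5.5 and 8 × √(32.852/19) = 10.5, so a shift of that size would not be noticed.

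It is also fair that the EMR is a named source, that PSSS tracks sedation state, that the data sheet is not reproduced, and that the data list is not exhaustive (it also omits PSSS and additional local anesthetic). So one cannot say sedative records will be unavailable, only that the visible text does not name them for extraction or use. PSSS gives a state, not a dose or a time.

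Finally, the Background section says additional sedative may follow, without a frequency. The assumed thresholds imply it on 23% to 50% of control sides, for which the documents offer no support.

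**Conclusion.** The concern holds in a limited form. Additional sedative may follow the signs under comparison, its time and amount are not named as data in the visible text, and the analysis does not say which readings it uses. The reason given for disregarding sequence does not cover a systemic sedative.

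Surgical-event readings may be pulled toward no difference. Second-side injection readings may move either way with order, with little net bias when order is balanced. It is tempting to treat first-side readings as safe, but that requires that no sedative comes between puncture and delivery, which the text does not establish.

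The true size is unknown. The bpm figures show direction and relative importance only, and rest entirely on the assumed means, SD, correlations, thresholds and damping. The gap is worth closing because closing it is cheap; it does not invalidate the study.

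**What to change.** No change to sedation care is needed.

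1. Data list and Study Procedures IV: add the time and amount of each additional sedative dose (from the EMR), any additional local anesthetic by side, and the order of sides and solutions.
2. Data Analysis Plan: make the puncture and delivery readings the main comparison, in line with the Objectives, in a within-child analysis that includes order. Report surgical-event readings separately.
3. Report additional sedative and additional local anesthetic by solution and order, descriptively.
4. Study Procedures I.3: confine the statement that sequence does not matter to nerve supply.

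Flagging readings taken after additional sedative is optional. Excluding them should not be presented as a better estimate, because it selects on a response that follows randomization and loses precision.

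The cost is EMR abstraction for 20 children, a few data-sheet fields, and possibly a minor amendment to the data list or authorization.

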### **Number of Research Participants**

We will enroll 20 children who were patients of the Rainbow Babies and Children's Hospital's (RBC) Tapper Dental Clinic or Dental Clinic of Rainbow Center for Women and Children.

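### Vital-sign changes are compared by an independent t-test with no defined reference, no pairing and no pre-solution covariate, which can cost precision in a 20-child split-mouth pilot

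*Combined protocol and SAP*

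**What the plan says.** The Data Analysis Plan will "compare the changes of vital signs, pain scores between buffered and conventional local anesthesia". For the method it says "we will use independent t-tests (SPSS v25", and for the threshold "We considered a P-value of 0.05 or less significant". It names no covariate, does not mention pairing, and does not say which reading a change starts from. It describes the variability as unknown and gives no standard deviation, correlation or power.

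The design is within-child. Study Design states "This is a prospective, single visit, randomized, double-blind split mouth study". Study Procedures, item I.1, adds "Both types of solution will be administered to each subject", and Number of Research Participants says "We will enroll 20 children".

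Study Procedures, item IV.1, offers two kinds of reference reading. Vital signs are "already recorded per standard of care at baseline and every 5 minutes, will be recorded manually for significant operative events", which suggests one baseline per child. The listed events include "topical anesthesia, injection (needle puncturing the oral mucosal tissues), delivery of both buffered and conventional local anesthesia", which suggests a reading just before each solution goes in. The text does not say that the puncture reading is kept separately for each side.

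**The concern.** A change score subtracts the whole reference reading, so it fixes the slope on that reference at one. That is efficient only when the reference tracks the later reading very closely; otherwise the reference's own noise is added to the outcome. Regression on the same reading estimates the slope from the data. Because solutions and sides are allocated at random, both approaches aim at the same contrast, so the choice between them is about precision.

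Precision is scarce with 20 children, and the planned test also ignores that each child supplies both readings. The plan further intends these data to inform the power calculation of a larger trial. Standard deviations of raw changes alone would not show whether adjustment could make that trial smaller.

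**Working it through.** **Inputs from the documents.** 20 children; both solutions in each child; independent t-test on changes; significance at 0.05 (two-sided assumed). The plan states no power, effect size or standard deviation, so it has no figure to reproduce.

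**Assumed.** Let r be the correlation, across children, between the buffered-minus-control difference in the pre-solution reading and the same difference at delivery. Take equal variances at the two times. The documents do not give r, so a range is shown.

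**Reading A: change from a same-side pre-solution reading, analysed in pairs.** Variances are relative to the uncorrected paired difference (= 1).

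- Change score: 2(1 − r).
- Covariate-adjusted: (1 − r²) × 18/17. The factor 1 + 1/(20 − 3) = 18/17 is the cost of estimating the slope.
- Ratio, adjusted to change: [(1 + r)/2] × 18/17.
- Children a change-score analysis would need to match: 20 / ratio.

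| r | Change score | Adjusted | Ratio | Children needed |
|---|---|---|---|---|
| 0.3 | 1.40 | 0.91 × 18/17 = 0.96 | 0.69 | 29.1 |
| 0.5 | 1.00 | 0.75 × 18/17 = 0.79 | 0.79 | 25.2 |
| 0.7 | 0.60 | 0.51 × 18/17 = 0.54 | 0.90 | 22.2 |
| 0.9 | 0.20 | 0.19 × 18/17 = 0.20 | 1.01 | 19.9 |

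Break-even is at (1 + r)/2 = 17/18, so r = 0.89. Below r = 0.5 the change score is less precise than making no correction at all.

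**Reading B: change from one baseline per child.** For child i, the difference between sides is (delivery on buffered side − baseline) − (delivery on control side − baseline). The baseline cancels and the paired variance is 1, so the fixed slope costs nothing. Adjusting for the same-side puncture difference gives (1 − r²) × 18/17, which is below 1 when r² > 1/18, that is r > 0.24. At r = 0.5 and 0.7 it gives 0.79 and 0.54.

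**Simulation check.** 20,000 trials of 20 children were run with illustrative between-child variance 60, within-child variance 40 and effect 5. None of these values comes from the documents.

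Power under reading A:

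| r | Independent t on change | Paired t on change | Within-child adjusted |
|---|---|---|---|
| 0.2 | 49% | 47% | 65% |
| 0.5 | 69% | 66% | 75% |
| 0.7 | 89% | 87% | 90% |
| 0.9 | about 100% | about 100% | about 100% |

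All three tests kept type I error near 5%.

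Under reading B, the planned independent t-test had type I error of about 0.7% and power of about 37%, against about 66% for a paired test. The reason is visible in the variances. Each change has variance 40 + 40 = 80, and the two sides share covariance 40 through the common baseline. The independent test works with 2 × 80/20 = 8 for the variance of the mean difference, where the true value is 2 × (80 − 40)/20 = 4.

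**The case against.** **The reference matters.** A reader might infer that subtraction loses precision whatever the reference. The documents do not support that. Item IV.1 makes a single baseline per child a natural reading, and under it the fixed slope has no cost once the data are paired. This objection stands, and it is why the conclusion is split by reading.

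**The per-side reading is inferred.** A reader might take the same-side pre-solution reading as already secured. Item IV.1 lists event types, not sides. Each side has its own puncture and delivery, so the inference is fair, but it needs to be written down.

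**The covariate may not be fully pre-treatment.** The second side is injected after the first in the same visit, so its puncture reading follows delivery of the other solution. Item I.3 calls sequence inconsequential because of separate nerve innervation, which does not address systemic vital signs. Adjustment therefore assumes no differential carryover into that reading. The assumption should be stated, but it does not favour subtraction, because a same-side change score needs it too.

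**The size is uncertain.** The 0.69, 0.79 and 0.90 compare two paired analyses, whereas the plan's test is unpaired, and r is unknown. They should not be quoted as the measured loss of the plan as written.

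**It is a pilot without a power target.** True, and no validity problem follows. But the change costs little, and estimating r is the kind of information a pilot can supply to its successor.

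**Conclusion.** The concern holds as a conditional loss of efficiency. The plan leaves the reference for a change undefined and uses neither the pairing nor a pre-solution covariate.

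- With a same-side reference, adjustment beats subtraction for r below about 0.89. The variance saving is 31%, 21% and 10% at r = 0.3, 0.5 and 0.7.
- With one baseline per child, the main loss comes from ignoring the pairing, and adjustment adds a further gain when r exceeds about 0.24.

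For r between about 0.24 and 0.89, adjustment is therefore better than the paired change under either reading. Outside that range it costs at most about 6% of variance (18/17 − 1).

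These figures assume equal variances at the two times, an assumed r, and a puncture reading that exists for each side. A reader might infer bias or an inflated false-positive rate. Neither follows: allocation is randomised, and in the simulation type I error was near 5% under reading A and well below it under reading B.

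**What to change.** **Data Analysis Plan.** Replace the independent t-test on vital-sign changes with a within-child analysis:

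1. For each child, compute the delivery difference (buffered minus control) and the same-side needle-puncture difference (buffered minus control).
2. Regress the first on the second, leaving the covariate uncentred.
3. Take the intercept, at a covariate difference of zero, with its 95% CI as the treatment estimate. Do not mean-centre the covariate: the intercept would then equal the unadjusted mean difference, and the adjustment would be lost.
4. Report the unadjusted paired difference and the observed r beside it.
5. State the assumption of no differential carryover from the first side into the second side's puncture reading.

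**Study Procedures, item IV.1.** State that the puncture reading is recorded separately for each side, before that side's solution is delivered.

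**Cost.** Analysis wording, a clarification on the data collection sheet, and one degree of freedom, worth at most about 6% of variance.

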## **Withdrawal of Research Participants**

Participants could be withdrawn from study without their consent in the event of an error which renders the data yielded inaccurate (for example, monitor malfunction, recording not applied at correct time).

Should participants be withdrawn, their data will be kept but not utilized for the study. All information will be kept in a HIPPA protected file as if they had continued, all privacy maintained in regards to study data.

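### Every child receives both solutions, yet the plan compares them with independent t-tests, so the error rate depends on an unknown within-child correlation

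*Combined protocol and SAP*

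**What the plan says.** The Study Design section reads: "This is a prospective, single visit, randomized, double-blind split mouth study". Study Procedures, item I.1, adds: "Both types of solution will be administered to each subject". Item I.3 has one side anesthetized with the solution chosen by coin flip, and then: "The provider will subsequently anesthetize the opposite side of the mouth with the opposite solution". The section on the number of participants sets enrollment at 20 children.

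The only analysis text is the Data Analysis Plan. For changes in vital signs and for pain scores it specifies a comparison "between buffered and conventional local anesthesia, we will use independent t-tests (SPSS v25"), with P of 0.05 or less counted as significant. It gives no power calculation because the variability is unknown, and then states: "The data from this study will provide the necessary information to perform a power analysis for a future, larger trial".

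No section mentions a paired test, a within-child difference, a mixed model or a within-child correlation.

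**The concern.** An independent t-test assumes that the buffered and control values come from unrelated children. Here each buffered value has a partner from the same child, the same sedation and the same monitor. Heart rate, blood pressure and respiratory rate are whole-child measurements, so the two sides can hardly be assumed unrelated.

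Two things are at stake. First, the 0.05 threshold no longer has a known meaning: the test is too conservative if rho is positive and too liberal if it is negative. Second, the pilot exists to supply inputs for a larger trial. If that trial is also split-mouth, its sample size depends on the SD of the within-child difference (or, equivalently, on rho), and the planned test reports neither.

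**Working it through.** The plan states no power or derived sample size, so there is no figure to reproduce. The check is whether the planned test delivers its nominal 5%.

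**Inputs from the documents.** 20 children, both solutions in each, independent t-test, alpha 0.05.

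**Assumptions.** Two-sided testing (sidedness is not stated); one value per child per side; normal outcomes with equal SD, sigma, on both sides; rho varied from -0.2 to 0.7; a true difference of 0.5 sigma for power.

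**Step 1: standard error.** The true variance of the mean difference is 2·sigma²·(1 - rho)/20. The independent test estimates 2·sigma²/20. The true SE is therefore sqrt(1 - rho) times the one the test uses, and the two agree only at rho = 0.

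**Step 2: approximate type I error.** This is 2·[1 - Phi(1.96/sqrt(1 - rho))].
- rho = -0.2: 1.96/1.095 = 1.79, giving 7.4%.
- rho = 0.5: 1.96/0.707 = 2.77, giving 0.6%.

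**Step 3: simulation with the t critical values.** 400,000 trials per setting; critical value 2.024 for the independent test (38 df) and 2.093 for the paired test (19 df).

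| rho | Type I error, planned | Power at 0.5 SD, planned | Power at 0.5 SD, paired |
|---|---|---|---|
| -0.2 | 7.3% | 35% | 28% |
| 0 | 5.0% | 34% | 32% |
| 0.3 | 2.1% | 31% | 43% |
| 0.5 | 0.8% | 29% | 56% |
| 0.7 | 0.1% | 25% | 78% |

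The paired test holds 5.0% at every rho. Its power was confirmed with the noncentral t distribution, with noncentrality 0.5·sqrt(20)/sqrt(2(1 - rho)). At rho 0.5 this is 0.5 × 4.472/1 = 2.24, giving 56.5%. The two tests have equal power, about 33.5%, at rho near 0.04. The planned test's higher power at rho -0.2 comes from its inflated error.

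**Step 4: interval width.** The ratio of the planned to the paired 95% interval is about (2.024/2.093)/sqrt(1 - rho): 1.16 at rho 0.3, 1.37 at 0.5 and 1.77 at 0.7. The plan promises no interval, so this applies to any that is reported.

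**Step 5: what rho might be.** The outcome is a change, so rho depends on the baseline. Study Procedures, item IV.1, describes "Vital signs, which are already recorded per standard of care at baseline and every 5 minutes" with further readings at operative events, but does not say which reading is the baseline for each side. Suppose all readings in a child have variance 1 and common correlation r.
- One shared baseline: Var(change) = 2(1 - r) and Cov = 1 - r, so rho = 0.5 for any r below 1.
- Separate baselines: Cov = r - r - r + r = 0, so rho = 0.

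Negative rho is also possible. The Background says that a reaction to injection "may lead to administration of additional sedative medications during treatment", which could blunt the response on the second side.

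**The case against.** The mismatch between design and test cannot be argued away, but four points on its size and weight deserve an answer.

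1. **The loss rests on an unknown rho.** With separate baselines and equal correlations rho is zero, and the planned test is then correct and slightly more powerful (34% against 32%). This stands. The power figures illustrate what could happen over a range; they do not measure actual harm.
2. **The conservative direction assumes one value per side.** Item IV.1 of Study Procedures lists several operative events, and the plan states no unit of analysis. If four events per side were pooled as separate observations, type I error could be about 9% or about 18%, or stay conservative at about 3%, depending on how variance splits between child, side and event (assumed splits 0.3/0.2/0.5, 0.1/0.4/0.5 and 0.5/0.1/0.4). This stands as a condition on the table above. It is also a further reason to fix one summary value per side.
3. **It is a pilot.** It has no stated power to lose, and rho can be computed later from the raw data. But the plan attaches a significance threshold to this test, and choosing the method after seeing the data is what a prespecified analysis should prevent.
4. **Separate nerve supply makes the sides independent.** The protocol uses that argument only to dismiss injection order. It does not make two sets of vital signs from one child independent.

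**Conclusion.** The plan is wrong as written. Its only named test assumes independence that its own design rules out, and this does not depend on any assumed number. The size does. With one value per side, normal data and equal SDs, the true error runs from 7.3% to 0.1% as rho goes from -0.2 to 0.7, and at rho 0.5 the planned test has about half the power of the paired one (29% against 56% for 0.5 SD). The documents do not fix the direction. Positive rho is plausible because both sides share the child and the sedation, and a null result would then be hard to interpret. The estimated mean difference is the same under either test when all pairs are complete; the standard error, P-value and any interval are not. The change should be made before the data are analyzed.

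**What to change.** Replace the independent t-tests in the Data Analysis Plan with text such as:

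> Paired t-tests on the within-child difference (buffered side minus control side), using one summary value per child per side for each operative event compared. The events compared and the baseline used for each change are named in advance. For pain scores, the Wilcoxon signed-rank test on the same pairs is a sensitivity analysis. The mean within-child difference, its 95% CI, the SD of the differences and the within-child correlation are reported for each outcome.

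The essential parts are the paired test, the single value per side, and reporting the SD of the differences and rho. The Wilcoxon test is a sensible addition because pain scores are ordinal.

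The cost is a few sentences. No extra children, data or software are needed, since SPSS v25 runs both tests. If rho is close to zero, power falls by about 2 points (32% against 34% at 0.5 SD). Under negative rho the paired test gives up only the power that the planned test gained from its inflated error. Pairing discards no half-pairs from withdrawn children, because the withdrawal section already says: "Should participants be withdrawn, their data will be kept but not utilized for the study". A child who stays in the study with one side's reading missing would drop out of the paired t-test, and the plan should say how many such children there are.
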